the principles of Good Clinical Pract Research, the Declaration of Helsin Medicines for Human Use (Clinica subsequent amendments, and ICH Choice of Control Groups.	search protocol plan will be conducted in accordance with tice, the UK Policy Framework for Health and Social Care ki, and the current regulatory requirements, including the I Trials) Regulations 2004 (UK S.I. 2004/1031) and all E9 - Statistical principles for Clinical Trials and ICH E10 - e statistical work in this protocol is accurate, and for the this study.			
Statistician's name:	[name]			
Signature:				
Date:				
Principal Investigator Agreement				
The clinical study as detailed within this research protocol (Version 2.0, dated 21/01/2025), or any subsequent amendments, involves the use of an investigational medicinal product and will be conducted in accordance with the UK Policy Framework for Health and Social Care Research , the World Medical Association Declaration of Helsinki (1996), Principles of ICH-GCP, and the current regulatory requirements, as detailed in the Medicines for Human Use (Clinical Trials) Regulations 2004 (UK S.I. 2004/1031) and any subsequent amendments of the clinical trial regulations.				
Principal Investigator name:	[name]			
Principal Investigator affiliation:	Barts Health NHS Trust			
Signature:				
Date:				

IV. Synopsis

Full title	Hospital-acquired Infection Prevention with Parenteral Omegaven		
Short title and / or acronym	HIPPO		
Sponsor	Queen Mary University of London		
MHRA Risk level	Type B, licenced product in the EU, used for new indication and in a new patient population		
Phase of the trial	Phase I/II		
Medical condition or disease under investigation	Patients admitted to Adult Critical Care Unit		
Study design and methodology	Single-centre randomised controlled dose-escalation trial		
Planned number of participants	36 participants		
Objectives	 Primary objective To determine the maximum tolerable dose of Omegaven that can be administered in critically ill patients. Exploratory objectives To measure omega-3 index and fatty acid profile To characterise immune profiles and function To characterise metabolic profiles 		
Inclusion and exclusion criteria	 Patients aged 18 years and over. Patients requiring intubation and ventilation OR requiring two or more other organ systems support (Sequential Organ Failure Assessment (SOFA) score ≥2 in >2 domains) without requiring intubation and ventilation. Patients predicted to remain in critical care unit for at least 72 hours as determined by the Intensive Care Consultant with clinical responsibility for patient care. Exclusion criteria (as defined in the patient's medical notes): Patients requiring total parenteral nutrition at time of enrolment or during the first 10 days Palliative care admission for end-of-life care or withdrawal of active therapy as determined by the Intensive Care Consultant with clinical responsibility for patient care 		

	Neutropaenia (<1x109/l) on admission to the Adult Critical	
	Care Unit	
!	Lymphopenia (<0.25x10 ⁹ /l) on admission to the Adult Critical	
	Care Unit	
	Primary immune deficiency	
	Bone marrow transplant recipient	
!	All immunosuppressive drug therapy (with the exception of	
	corticosteroid use for acute illnesses in the preceding five	
!	days)	
	Recorded or reported allergy to fish, or egg protein or to any	
	of the active ingredients or excipients	
!	Known inborn errors of lipid metabolism	
	Recorded or reported severe hyperlipidaemia or severe	
!	disorders of lipid metabolism (Electronic health record	
!	documentation ± clinical concern and if available with serum	
	triglycerides >400 mg/dl on admission to the Adult Critical	
	Care Unit	
!	 Enrolment in any other study with an IMP or a study that 	
	may have similar primary outcome	
	Therapeutic anti-coagulation therapy	
!	 Pregnancy 	
!	The absence of the above criteria in the medical notes will be	
	considered to indicate no concern	
	Patients in the intervention arm will receive intravenous	
Investigational Medicinal	Omegaven in three different doses (dose-escalation: 0.2, 0.4	
Product(s)	and 0.6 g/kg/day)	
	Patients in the control arm will receive standard care	
Treatment duration	10 days or hospital discharge, whichever happens sooner	
Follow-up duration	30 days from start of intervention	
End of trial definition	This is defined as the date when the last patient's blood sample	
End of that definition	has been analysed	

1.0 Introduction

1.1 Background

Hospital-acquired infections (HAI) are new infections that are typically not present at admission and manifest 48 hours after hospital admission. HAIs include central line-associated bloodstream infections, catheter-associated urinary tract infections, surgical site infections, hospital-acquired pneumonia, ventilator-associated pneumonia, and *Clostridium difficile* infections. The National Institute for Health and Care Excellence (NICE) estimates 300,000 patients a year in England acquire a HAI as a result of care within the NHS, with an estimated cost of £1 billion/year (NICE CG139). HAIs are not only a public health issue but also a major, patient safety concern, monitored by the National Care Quality Commission. Larope wide, 2.5 million HAIs are reported yearly with > 90,000 attributed deaths.

Critically ill patients (with or without COVID-19) are more susceptible to HAIs with an incidence of ventilator acquired pneumonia in non-COVID-19 patients of approximately 15-20%.⁶⁻⁸ This proposal seeks to prevent HAI in critically ill patients using administration of omega-3 fatty acids (FAs). Critically ill patients are often in a catabolic state, with intense metabolic changes, leading to energy deficits, malnutrition, and impaired immune system function.9 Therefore, medical nutrition therapy needs to be considered for all patients staying in the critical care unit for more than 48 hours. Although oral or enteral nutrition is preferred, often patients will receive parenteral nutrition or total parenteral nutrition. Lipid emulsions should generally be part of parenteral nutrition in critical care but should not exceed 1.5 g lipids/kg/d, according to the latest European Society for Clinical Nutrition and Metabolism (ESPEN) guidelines. 10 Emulsions solely based on soybean oil, rich in omega-6 FAs, should be avoided due to their likely proinflammatory effects. Currently, there is no specific recommendation for lipid emulsions containing omega-3 FAs; however, the guidelines allow parenteral lipid emulsions enriched with eicosapentaenoic acid (EPA) and docosahexaenoic acid (DHA) (fish oil dose 0.1 - 0.2 g/kg/d) to be used, indicating that they are safe to use and well tolerated. Therefore, omega-3 FA containing lipid emulsions can be part of the parenteral feeding scheme; however, they can also be used as an additional "drug". In the LIPIDS-P trial, a similar intravenous lipid emulsion containing 15% fish oil was tested for the first time as therapeutic intervention in patients with sepsis and septic shock, rather than as a nutritional intervention.¹¹

1.2 Rationale for study design

Several studies highlight the potentially beneficial effects of using omega-3 FAs in critically ill patients. A systematic review from 2012 investigating the effect of omega-3 FA supplementation on inflammatory biomarkers concluded that dietary omega-3 FAs are

associated with lower plasma levels of inflammation and endothelial activation. However, the quality of the included studies was deemed low. A few trials including 159 medical and surgical patients across 17 Spanish critical care units found a significant reduction in nosocomial infections and predicted time free of infections in patients receiving total parenteral nutrition prepared with a lipid emulsion containing 10% fish oil (0.1 g fish oil/kg/d). A recent (2020) systematic review with meta-analysis concluded that omega-3 FA enriched lipid emulsions should be preferred over standard lipid emulsions, due to the reported benefits of shortening the length of hospital stay and length of critical care stay by two days, and reducing the risk of sepsis. Similar results were found for critically ill patients. In patients of the sepsion of the results were found for critically ill patients.

Due to the anti-inflammatory properties, omega-3 FAs may be useful as a therapeutic agent in critically ill patients, preventing them from HAIs. These immunomodulatory effects have been shown in clinical trials in critically ill and surgical patients. However, the acceptable dose that needs to be administered and is tolerated by patients' needs to be determined. This will be clarified in a dose-escalation randomised controlled trial. Inclusion of a control (standard care) group will provide information on expected baseline levels of the outcomes.

1.3 Assessment and management of risk

This trial is categorised as Type B (studies that testing authorised medicinal products according to treatment regimens outside the marketing authorisation) hence this is somewhat higher than the risk of standard medical care.

The investigational medicinal product (IMP) for the HIPPO trial is Omegaven, a licensed product in the EU used for parenteral nutritional supplementation (MA34164.00.00), with long chain omega-3 fatty acids, when oral or enteral nutrition is impossible, insufficient or contraindicated. In the USA Omegaven is also used in paediatric patients with parenteral nutrition-associated cholestasis.

Previously, Omegaven has been used nutritionally in critically ill patients (0.15 g/kg/d – 0.2 g/kg/d) in the EU. ^{17 18} In the UK, Omegaven has also been used therapeutically in clinical trials to improve clinical outcomes in critically ill patients with sepsis ¹⁹ and patients with severe advanced esophagogastric adenocarcinoma receiving palliative chemotherapy, ²⁰ and perioperatively in patients undergoing liver surgery. ²¹ In Taiwan, Omegaven has also been used therapeutically in critically ill patients with sepsis (10 g/d for 5 days) ²². In this trial, it will be used for a new indication (therapeutic intervention instead of nutritional support) in a new population (critically ill patients). Therefore, this trial will determine the maximum tolerable dose, across three pre-specified doses, in the critically ill patient population. For most parts, the current Summary of Product Characteristics (SmPC) will be followed, however, patients

with life-threatening conditions, which are listed as contraindication in the SmPC, will not be excluded, since this trial seeks to specifically test the safety of Omegaven in this new patient population. To minimise any risks, all patients enrolled in HIPPO will be inpatients during the intervention and will be monitored throughout their hospital stay.

The route of administration (intravenous; central or peripheral) is defined in the SmPC for the IMP. The lowest proposed dose (0.2 g/kg/d of Omegaven) is based on the ESPEN guidelines.¹⁰ A dose of 0.4 g/kg/d of Omegaven was chosen as a step wise change. The rationale for using 0.6 g/kg/d of Omegaven as the highest dose is that it has been used previously in a clinical trial in critically ill patients in Turkey.²³ This dose is also to prevent lipid overload syndrome or parenteral nutrition-associated liver disease.

For safety reporting all patients receiving the IMP will be assessed at least until five hours after the last infusion has stopped. This is based on 1) the triglyceride half-life for Omegaven being 54 minutes according to the SmPC and 2) the Council for International Organisations of Medical Sciences recommendation to collect Adverse Events (AEs) for at least an additional five half-lives of the IMP, after IMP administration.²⁴

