2.4 Exploratory laboratory data

Exploratory laboratory data will be collected to characterise the following in comparison to control blood samples:

- The immune profiles (proportion of T-cells, B-cells, monocytes, natural killer cells and neutrophils) and function (including cytotoxicity and antibody production) using flow cytometry before the start of intervention and on day five, 10 and 20 after the start of intervention
- The metabolic profiles (i.e. cytokine production using electro-chemiluminescence and cell metabolic analysis using Seahorse) after treatment with Omegaven in comparison to control blood samples before the start of intervention and on day five, 10 and 20 after the start of intervention.
- Omega-3 Index (% Eicosapentaenoic Acid + Docosaheaxaenoic Acid of total fatty acids) and Fatty Acid (FA) profile (Myristic, Palmitic, Palmitelaidic, Palmitoleic, Stearic, Elaidic, Oleic, Linoelaidic, Linoleic, Arachidic, gamma-Linolenic, Eicosenoic, alpha-Linolenic, Eicosadienoic, Behenic, Dihomo-g-linolenic, Arachidonic, Lignoceric, Eicosapentaenoic, Nervonic, Docosatetraenoic, Docosapentaenoic-n6, Docosapentaenoic n3, and Docosahexaenoic acid) will be measured in blood samples collected before the start of intervention and on day five, 10 and 20 after the start of intervention to be measured at an external laboratory (OmegaQuant).

These data are not part of the core objectives for the HIPPO trial but will provide mechanistic data that would inform a future efficacy trial.

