8.1 Schedule of treatment and assessments for each visit

The trial intervention period will commence on the day of randomisation and finish with the 30-day follow-up.

	Within 48 hours	n 48 hours Days from start of intervention													
Assessment/ investigations	of critical care admission/ Day 1 of intervention	2	3	4	5	6	7	8	9	10	11	20	30		
Eligibility review	Х														
Patient informed consent or by Professional/ Personal Legal	x														
Representative *															
Randomisation	Х														
Omegaven administration	х	х	х	х	х	х	х	х	х	х					
DLT events and safety review	х	х	х	х	х	х	х	х	х	х	х				
Trial blood sample	X [#]				Х					Х		Х			
Follow-up in ward/telephone call													Х		
Medical record review	х	х	х	х	х	Х	Х	х	х	х	х		Х		

HIPPO V3.0 14/02/2025 Page 34 of 62

^{*} Patient consent will be obtained when the patient regains the capacity to consent

[#] before intervention begins

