11.13 Concomitant medication

The infusion of Omegaven can cause a prolonged bleeding time and an inhibited platelet aggregation. Therefore, Omegaven should be administered with caution to patients requiring anticoagulant therapy, even with regard to a possible reduction of anticoagulants. Incompatibilities may also occur through the addition of polyvalent cations, e.g. calcium, especially when combined with heparin. Full details of interaction with medicinal products and other forms of interaction can be found in the SmPC. Patients will be closely monitored for any harms during the course of the intervention.

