15.9 Safety analysis

Frequencies and type of AEs will be recorded for each randomised group (control and intervention), and each dose level of Omegaven.

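### The protocol sets no common end to adverse-event collection: days 12-30 have no scheduled safety review, and observation time may differ by arm and by early stopping.

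*Protocol*

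**What the plan says.** Section 1.3 gives the safety-reporting window for treated patients: "For safety reporting all patients receiving the IMP will be assessed at least until five hours after the last infusion has stopped". It offers two reasons: "the triglyceride half-life for Omegaven being 54 minutes according to the SmPC", and a recommendation to "collect Adverse Events (AEs) for at least an additional five half-lives of the IMP". The same section says that inpatients "will be monitored throughout their hospital stay".

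Other sections give different end points or none:

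- **2.6 (DLT assessment):** screening in the Omegaven arm ends five hours after the last dose, or at discharge if that is earlier. Controls are screened over days 1-11 so that event rates can be compared.
- **8.1:** the row "DLT events and safety review" is marked on days 1 to 11 and not on day 20 or day 30. A medical record review is marked on days 1-11 and on day 30.
- **8.2:** safety review is listed for days 1-10 or to discharge. The day-30 call covers antibiotics, supplement use and ethnicity. The routinely collected data include infections, mortality, laboratory values and transfusions.
- **13.4:** non-exempt AEs are recorded and followed to resolution, with no end date for detecting them.
- **15.9:** "Frequencies and type of AEs will be recorded for each randomised group (control and intervention), and each dose level of Omegaven". No time limit is stated.

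The synopsis sets follow-up at 30 days from the start of intervention.

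**The concern.** An AE table by arm and dose can be read only if each group was observed in the same way for the same time. Here the one explicit AE window is tied to each treated patient's last infusion, and a control has no infusion to end it. If site staff work to that minimum, a patient taken off Omegaven early is observed for less time than a control. The shortfall is largest at any dose that is stopped more often.

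The rationale also covers only part of what the trial studies. The 54-minute figure describes clearance of infused triglyceride. Section 2.4 follows the fatty acids themselves, which "will be measured in blood samples collected before the start of intervention and on day five, 10 and 20 after the start of intervention", and immune function on the same days. Section 11.13 warns: "The infusion of Omegaven can cause a prolonged bleeding time and an inhibited platelet aggregation". The plan looks for biological effects at day 20 but schedules no safety review then. This is an open-label trial whose stated purpose is safety in a new population, so it should not be left to judgement when AE detection stops.

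**Working it through.** **1. The plan's own figure.** Five half-lives: 5 x 54 min = 270 min = 4.5 h, rounded up to 5 h. Fraction of triglyceride left at 5 h: 0.5^(300/54) = 0.021, about 2%. The five-hour figure reproduces.

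**2. Consistency with the schedule.** Section 7.0 gives a rate of 0.5 ml/kg/h, and the product contains 10 g per 100 ml (0.1 g/ml). Infusion time = (dose / 0.1) / 0.5, which is 4, 8 and 12 h for 0.2, 0.4 and 0.6 g/kg/d. A day-10 infusion plus five hours can run into day 11, so the day-11 mark in 8.1 fits the five-hour minimum. The day-10 entry in 8.2 does not match it.

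**3. Days without scheduled review.** 30 - 11 = 19 days (days 12-30); 19/30 = 63%.

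**4. End points side by side.**

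| Section | Omegaven | Control |
|---|---|---|
| 1.3, safety reporting | at least 5 h after last infusion | not stated |
| 2.6, DLT screening | 5 h after last dose, or discharge | days 1-11 |
| 8.1, safety review | days 1-11 | days 1-11 |
| 8.2, safety review | days 1-10 or discharge | days 1-10 or discharge |
| 13.4, AE recording | no end date | no end date |

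For a patient whose last infusion is on day 3, the 1.3 minimum expires about eight days before the 8.1 schedule ends (11 - 3 = 8).

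**5. Illustrations only.** The protocol gives no hazard shape, so a constant hazard is assumed.

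- *Share of 30-day events after day 11.* Section 15.1 gives mortality of 20-30% without a time horizon; assume it applies to 30 days. Share = 1 - [1 - (1 - m)^(11/30)]/m. For m = 0.20 this is 0.61, and for m = 0.30 it is 0.59. This is little more than the calendar share (63%) restated.
- *Early stopping, if the minimum were used as the end.* Take a true risk of 30% by day 11. The risk seen by day s is 1 - 0.70^(s/11): 0.093 for s = 3 and 0.150 for s = 5. The apparent fall from 30% to 9% or 15% comes from observation time alone.

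**6. Half-life of the fatty acids.** The documents give none for incorporated EPA and DHA. If it were 1, 3, 7 or 10 days, five half-lives would be 5, 15, 35 or 50 days. These values are assumptions and serve only to show that a window based on half-life depends on which component is chosen.

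**The case against.** The strongest reply is that five hours is a floor. Section 1.3 says as much, it promises monitoring for the whole hospital stay, 13.4 and 13.7 give no end date, and 15.9 has no time cut. A reader might infer that AE collection is cut at five hours and that later harm is missing from the safety analysis. The documents do not support that. Deaths, infections, transfusions and laboratory values are on the record-review list, and a record review takes place at day 30.

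The early-stopping bias is likewise conditional. The 8.1 schedule does not make daily review depend on continued dosing, and section 9.0 continues record collection after withdrawal unless it is declined. The 9% and 15% figures arise only if the floor is used as a ceiling.

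A reader might also take the day-20 samples as evidence that late toxicity is expected. They are exploratory and show only that effects are looked for. Section 11.13 ties the bleeding and platelet effects to the infusion.

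All of this stands, but it does not supply an end point. Following an event to resolution requires that it has been detected, monitoring during the stay ends at discharge, and 15.9 can tabulate only what was captured. Nothing says that the outcomes taken from the notes enter the safety tables.

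**Conclusion.** The point holds as a gap in ascertainment: no common end of AE/SAE collection is fixed, and the sections that bear on it disagree. Days 12-30, 19 of 30 follow-up days, have no scheduled AE review and no listed AE question in the call. Late events may therefore be picked up unevenly, and observation time may differ by arm and by early stopping. The size and direction of any resulting bias cannot be derived from the documents; the figures of about 60%, 9% and 15% are illustrations under a constant hazard.

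The maximum tolerable dose does not change, because it rests on DLTs. What is affected is the AE comparison by arm and dose that will be reported beside it. A correction is worthwhile because it is cheap and safety is the purpose of the trial.

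**What to change.** Reconcile 1.3, 2.6, 8.1, 8.2 and 13.4. State one AE/SAE data-collection window for both arms, from randomisation to day 30, regardless of when Omegaven stops. Fill it from the day-30 record review already scheduled and one AE question added to the call already planned.

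In 15.9, tabulate AEs and SAEs to day 11 and to day 30, by dose and concurrent control. Add the deaths, transfusions and liver tests already collected from the notes. These extra rows are needed because 13.6 exempts several relevant events from AE reporting, among them transient liver-test rises, pneumonia, sepsis and worsening organ failure, so a longer window alone would not bring them into the tables.

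The cost is protocol wording, one question and some table rows, plus more event recording between day 11 and day 30, much of it likely to reflect critical illness. No new visit is needed. The change concerns data collection only and leaves clinical monitoring and treatment rules as they are.

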2.0 Trial objectives

2.1 Primary objective

 To determine the maximum tolerable dose of Omegaven that can be administered in critically ill adults

2.2 Exploratory objectives

- To measure Omega-3 Index and fatty acid profile
- To characterise immune profiles and function
- To characterise metabolic profiles

2.3 Primary outcome measure

• The primary outcome measure is the maximum tolerable dose of Omegaven, across three pre-specified doses (0.2, 0.4, 0.6 g/kg/d) which will be calculated after the completion of the dose-escalation (see section 2.6 and 7.0 for further details).

2.4 Exploratory laboratory data

Exploratory laboratory data will be collected to characterise the following in comparison to control blood samples:

- The immune profiles (proportion of T-cells, B-cells, monocytes, natural killer cells and neutrophils) and function (including cytotoxicity and antibody production) using flow cytometry before the start of intervention and on day five, 10 and 20 after the start of intervention
- The metabolic profiles (i.e. cytokine production using electro-chemiluminescence and cell metabolic analysis using Seahorse) after treatment with Omegaven in comparison to control blood samples before the start of intervention and on day five, 10 and 20 after the start of intervention.
- Omega-3 Index (% Eicosapentaenoic Acid + Docosaheaxaenoic Acid of total fatty acids) and Fatty Acid (FA) profile (Myristic, Palmitic, Palmitelaidic, Palmitoleic, Stearic, Elaidic, Oleic, Linoelaidic, Linoleic, Arachidic, gamma-Linolenic, Eicosenoic, alpha-Linolenic, Eicosadienoic, Behenic, Dihomo-g-linolenic, Arachidonic, Lignoceric, Eicosapentaenoic, Nervonic, Docosatetraenoic, Docosapentaenoic-n6, Docosapentaenoic n3, and Docosahexaenoic acid) will be measured in blood samples collected before the start of intervention and on day five, 10 and 20 after the start of intervention to be measured at an external laboratory (OmegaQuant).

These data are not part of the core objectives for the HIPPO trial but will provide mechanistic data that would inform a future efficacy trial.

